9 ELIGIBILITY

9.1 Enrollment Criteria

9.1.1 Inclusion Criteria

1. Only subjects that were enrolled and met the inclusion criteria for the Cingal 16-02 trial and signed the informed consent are eligible for Cingal 17-02.
2. Subject is able to understand and comply with the requirements of Cingal 17-02 and voluntarily provides consent.

Patients will not be rescreened at enrollment to Cingal 17-02 as these patients were enrolled and met the inclusion / exclusion criteria for the Cingal 16-02 clinical trial. All patients enrolled in the Cingal 16-02 trial will be eligible to participate in Cingal 17-02.

For reference only, the inclusion criteria used in Cingal 16-02 were:

1. Subject is 40-75 years old, with a Body Mass Index (BMI) $\leq 40 \text{ kg/m}^2$.
2. Subject has Kellgren-Lawrence (K-L) severity grade I, II or III in the index knee as determined by X-ray. Contralateral knee: K-L severity grade 0, I or II.
3. Subject has had at least two signs and at least two symptoms of OA disease (based on the European League Against Rheumatism (EULAR) recommendations for diagnosing knee OA in the index knee for at least 6 months despite conservative treatment (weight reduction, physical therapy, pain medications, etc.). The EULAR signs and symptoms are as follows:
 - a. Signs: crepitus, restricted movement and bony enlargement
 - b. Symptoms: persistent knee pain, limited morning stiffness and reduced function

4. Subject must be willing to abstain from other intraarticular (IA) treatments of the knee for the duration of the study.
5. Subject is willing to discontinue all analgesics including NSAIDs, except acetaminophen/paracetamol, at least seven days before the treatment injection and through the completion of the study.
6. Subject is willing to use only acetaminophen/paracetamol (up to a maximum of 4.0 grams per day per the package insert) for the treatment of joint pain for the duration of the study. At least forty eight hours prior to the Baseline Visit and each follow-up visit, the subject is willing to discontinue use of acetaminophen/paracetamol.
7. Subject is willing to maintain a stable dose of oral glucosamine and/or chondroitin sulfate products throughout the study, if taken prior to signing the informed consent form (ICF).
8. Subject is able to understand and comply with the requirements of the study and voluntarily provides consent.

9.1.2 Exclusion Criteria

Patients will not be rescreened at enrollment to Cingal 17-02 as these patients were enrolled and met the inclusion / exclusion criteria for the Cingal 16-02 clinical trial.

Only patients enrolled in the Cingal 16-02 trial will be eligible to participate in Cingal 17-02.

For reference only, the exclusion criteria used in Cingal 16-02 were:

9.1.3 Screening Exclusion Criteria in Cingal 16-02

1. Subject received an IA injection of Hyaluronic Acid (HA) and/or steroid in either knee within 6 months of signing the ICF. A subject will be excluded if they are planning to receive an HA or steroid injection (other than the study injection) in either knee during the course of this study.
2. Subject had an arthroscopy of either knee within 3 months of signing the ICF.
3. Subject had an open surgical procedure of either knee or hip or any surgery of the spine within 12 months of signing the ICF. Subject plans to have knee, hip or spine surgery within the study period.
4. Subject has intra-articular trauma to the index knee. Subject has concurrent multi-system or multi-limb trauma.
5. Subject has evidence or medical history of the following diseases in the index knee: septic

arthritis; inflammatory joint disease; history of Reiter's syndrome; gout; chondrocalcinosis associated with recurrent episodes of acute synovitis of the knee consistent with pseudogout; osteochondritis dissecans, Paget disease of the bone; ochronosis; acromegaly; hemochromatosis; primary osteochondromatosis; known history of Wilson disease; heritable disorders or collagen gene mutations.

6. Subject has a history of cartilage repair surgery in the index knee within 3 years of signing the ICF.
7. Subject has a history of ACL repair, reconstruction or injury in the index knee within 3 years of signing the ICF.
8. Subject has X-ray findings of acute fractures, severe bone loss, avascular necrosis, severe bone or joint deformity in the index knee.
9. Subject has significant varus or valgus deformity greater than 10 degrees in either knee.
10. Subject has a clinically apparent tense effusion of the index knee.
11. Subject has knee instability in either knee per the Investigator's assessment.
12. Subject requires consistent use of an assistive device (e.g. wheelchair, walker, etc.)
Occasional use of a cane is acceptable.
13. Subject has medical condition(s) which could affect study assessments or may adversely affect the safety and/or success of the study treatment. This includes but is not limited to the following:
 - a. Peripheral neuropathy severe enough to interfere with evaluation of the subject,
 - b. Vascular insufficiency severe enough to interfere with evaluation of the subject,
 - c. Active fibromyalgia,
 - d. Hemiparesis involving either lower extremity,
 - e. Immunocompromised or immunosuppressive disorder or receiving medications to treat immunosuppressive disorders,
 - f. Systemic bleeding disorder(s),
 - g. Current malignancy or treatment within the last 5 years, except for non-melanoma skin cancer,
 - h. Significant psychiatric disorder,
 - i. Active drug and/or alcohol abuse within the past year,
 - j. Uncontrolled diabetes with a screening HbA1c of >7%.
14. Subject is taking medications at the time of signing the ICF which could interfere with the treatment procedure, healing and/or assessments. This includes but is not limited to oral or injectable anticoagulant treatments, anti-aggregant platelet treatment, chronic opioid analgesics. Low dose aspirin used for cardiovascular protection is allowed if a stable regimen

is maintained for the duration of the study.

15. Subject is receiving treatment using electromagnetic stimulation and/or low intensity ultrasound in the index knee at the time of signing the ICF, within 3 months of signing the ICF or plans to receive treatment any time during the study period.
16. Subjects who had an oral, intramuscular, intravenous, rectal suppository or topical (excluded in index knee only) corticosteroid within 30 days of signing the ICF are excluded. Topical corticosteroid use at any site other than the index knee is allowed.
17. Subject has a pre-treatment contraindication to IA injections or aspiration of the index knee, including cutaneous infection in the injection site area, active IA infection (as suggested by moderate or marked effusion), knee deformity or condition which, in the opinion of the investigator could jeopardize the sterility or delivery of the IA injection.
18. Subjects with a history of hypersensitivity to any of the ingredients in the hyaluronan or previous hypersensitivity to the administration of corticosteroids or an inability to tolerate acetaminophen/paracetamol.
19. Subject has any contraindication to the receipt of corticosteroids.
20. Subject is receiving or in litigation for worker's compensation.
21. Subject is a woman who is pregnant or breastfeeding at the Screening Visit or a woman of child bearing potential who refuses to use effective contraception during the course of the study.
22. Subject was involved in any other research study involving an investigational product, or a new application of an approved product, within 60 days of signing the ICF.

9.1.4 Baseline Inclusion Criteria in Cingal 16-02

1. Subject has a Western Ontario and McMaster Universities Osteoarthritis Index (WOMAC) pain-sub-score ≥ 40 mm and ≤ 90 mm in the affected knee and ≤ 30 mm in the contralateral knee on a 100 mm Visual Analog Scale (VAS) scale.

9.1.5 Baseline Exclusion Criteria in Cingal 16-02

1. Subject has a decrease of ≥ 20 mm in the WOMAC pain-sub-score (average of 5 pain scales) from Screening to Baseline in the index knee on a 100 mm Visual Analog Scale (VAS) scale.
2. Subject has a synovial fluid aspirate volume > 20 mL in the index knee.
3. Subject has a contraindication to continue with the study treatment injection based on the visual appearance of the synovial fluid aspirate unless the fluid is examined microscopically prior to injection with no clinically significant findings (e.g. bacteria, crystals or blood).
4. Subject has ROM of less than 100° flexion in either knee.

10 STUDY PROCEDURES

10.1 Schedule of Events

	Pre-Treatment	Treatment		Post-Treatment Follow-Up Visits						17-02 Follow-Up Visits	
		Day 0 (7-14 days after screening visit)		1 week	3 weeks	6 weeks	12 weeks	18 weeks	26 weeks	Consent	39 Weeks
Assessments	-7 to -14 Days	Day 0 (7-14 days after screening visit)		1 week	3 weeks	6 weeks	12 weeks	18 weeks	26 weeks	Consent	39 Weeks
	Screening	Baseline	Treatment	±3 days			± 1 week				
Informed Consent	X									X	
Demographics Medical History	X										
Physical Exam, Vitals, BMI	X										
Urine / Blood Pregnancy Test	X										
Chemistry/Hematology/Urinalysis	X										
Bilateral Knee X-rays and assessment of K-L	X										
Review of X-rays by Independent Radiologist	X										
Physical Evaluation (Both Knees)	X	X		X	X	X	X	X	X		X
ROM (Index Knee)	X	X		X	X	X	X	X	X		X
ROM (Contralateral Knee)	X	X					X		X		X
WOMAC (Both Knees)	X	X		X	X	X	X	X	X		X
Evaluation of Enrollment Criteria	X	X	X							X	
Stop Analgesics/NSAIDs except Paracetamol	X										
Assess D/C Paracetamol ≥ 48 hours before Visit		X		X	X	X	X	X	X	X	X
Paracetamol Dispense/Pill Count	X	X		X	X	X	X	X	X	X	X
Distribute Subject Diary	X										X
Randomization			X								
Aspiration/ Evaluation of Synovial Fluid			X								
IA Injection			X								
Evaluate Diary		X		X	X	X	X	X	X		X
EuroQol		X		X	X	X	X	X	X		X
Patient Global Assessment		X		X	X	X	X	X	X		X
Evaluator Global Assessment		X		X	X	X	X	X	X		X
Concomitant Medication Assessment				Throughout the study							
Adverse Event Assessment				Throughout the study							

† -Cells in grey indicate assessments conducted only during Cingal 16-02 trial.

10.2 Procedure Description

10.2.1 Informed Consent Form (ICF)

The subject will be asked to sign the ICF prior to attending the 39 week follow up visit.

All data collected in the clinical trial Cingal 16-02 will be utilized in Cingal 17-02. The demographics and assessments conducted at screening and baseline for Cingal 16-02 will be utilized as the demographic and baseline data for Cingal 17-02.

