3 STUDY SYNOPSIS

Title	Extension Study to Cingal 16-02: Trial Extension to 39 Week Follow Up in the Randomized, Double-Blind, Active Comparator Controlled, Multi-Center Study of a Single Injection Cross-Linked Sodium Hyaluronate Combined with Triamcinolone Hexacetonide (Cingal) to Provide Symptomatic Relief of Osteoarthritis of the Knee
Study Objective	To evaluate the efficacy and safety of a single injection of Cingal for relief of joint pain at 39 week follow up in subjects with Osteoarthritis (OA) of the knee who have not responded to conservative treatment.
Investigational Product	Subjects enrolled in Cingal 17-02 will not receive an injection. For reference only, the investigational product utilized in Cingal 16-02 was: Cingal : A chemically cross-linked sodium hyaluronate supplied as a 4-mL unit dose with a nominal 18 mg of triamcinolone hexacetonide (TH) in a 5-mL glass syringe.
Comparator Product	Subjects enrolled in Cingal 17-02 will not receive an injection. For reference only, the comparator products utilized in Cingal 16-02 were: Triamcinolone Hexacetonide (TH) : 20 mg/ml supplied as 1 mL unit dose in a glass ampoule. Monovisc® : A chemically cross-linked sodium hyaluronate supplied as a 4-mL unit dose in a 5-mL glass syringe.
Mode of Delivery	For reference only, the mode of delivery in Cingal 16-02 was: Cingal, Triamcinolone Hexacetonide, or Monovisc will be injected into the intraarticular (IA) space of the index knee using an 18-21 gauge needle.
Study Design	Multi-center, randomized, double-blind, parallel group, 3-arm, active comparator controlled study
Phase	Phase III
Sample Size	A total of 576 subjects will be enrolled. This equates to 256 subjects injected with Cingal, 256 subjects injected with Monovisc and 64 subjects injected with TH. All subjects who meet enrollment criteria and completed the 26 week follow up in Cingal 16-02 will have the option to participate in the sub-study.
Study Duration	The entire sub-study duration will be an additional 13 weeks. The follow up visit will be scheduled at 39 weeks post treatment.

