7.2 Secondary Efficacy Endpoints

- The change from baseline in knee pain as measured by the WOMAC Pain Score (100 mm VAS) at 39 weeks post treatment comparing the Cingal group to the TH group.
- The change from baseline in WOMAC Physical Function score at 39 weeks post treatment comparing the Cingal group to the TH group.
- The change from baseline in WOMAC Stiffness score at 39 weeks post treatment comparing the Cingal group to the TH group.
- The change from baseline in Total WOMAC score at 39 weeks post treatment comparing the Cingal group to the TH group.
- The change from baseline in the Patient Global Assessment 39 weeks post treatment in the Cingal group compared to the TH group.
- The change from baseline in the Evaluator Global Assessment at 39 weeks post treatment in the Cingal group compared to the TH group.
- The usage of rescue medication through 39 weeks post treatment in the Cingal group compared to the TH group.

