10.2.12.2 Rescue Medications

Acetaminophen/paracetamol (up to a maximum of 4.0 grams per day per the package insert or as per regional limitations) will be allowed as the rescue medication for the treatment of joint pain for the duration of Cingal 17-02. At least forty eight hours prior to the 39 week follow-up visit the subject should discontinue use of the rescue medication.

At the Screening Visit for Cingal 17-02, the rescue acetaminophen/paracetamol specifically labelled for use within Cingal 17-02 will be dispensed. The rescue medications provided to the subject for Cingal 16-02 should be returned to the investigational site at the Cingal 16-02 26 week follow up visit.

The subject should be instructed to bring the rescue medication with them to 39-week follow-up visit for a pill count. Additional rescue acetaminophen/paracetamol will be dispensed as needed only if there is an unscheduled the follow-up visit before the 39 week follow up visit.

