10.2.12.3 Concomitant Medications

A medication is considered concomitant if taken after signing the ICF and up to and including the 39 week follow-up visit. Data on medications will include: medication name, dose, unit, route, frequency, start date, stop date, indication and whether the medication was taken for an AE.

At each study visit, the subject will be asked about any new medications that were started since the last visit. Indications for any new medications during the study period will be recorded as AEs, unless the medications are administered for a pre-existing condition.

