10.4 Post-Treatment Follow-Up

All study subjects will have follow-up assessments at 39 weeks after injection day in Cingal 16-02 to evaluate effectiveness of the treatment and to assess AEs and protocol compliance. The Blinded Evaluator will evaluate the clinical status of the subject at each visit.

More than 48 hours prior to the visit, the subject will be reminded of the visit date and time, the need to abstain from acetaminophen/paracetamol for at least 48 hours prior to each follow-up visit and the requirement to bring their subject diary and the acetaminophen/paracetamol for a pill count with them to the appointment.

If the subject arrives for a study visit without discontinuing acetaminophen/paracetamol for at least 48 hours prior to the visit, the visit should be rescheduled within the allowed window of time. Study assessments should be performed as soon as possible and the protocol deviation, if applicable, recorded in the source and eCRF. The subject must be re-educated about the importance of protocol compliance.

If the subject does not come in at the expected time, at least three attempts will be made to contact the subject in order to accomplish maximum subject compliance with the follow-up schedule.

The following post-treatment visits will be performed. The subject will be asked whether any concomitant medications have been taken. All assessments will be done by the Blinded Evaluator.

39 Weeks \pm 7 Days

- Confirm Rescue Medication Washout
- Evaluate Subject Diary
- Count Rescue Medication Pills (if needed)
- Physical Evaluation (both knees)
- ROM (both knees)
- WOMAC (both knees)
- Patient Global Assessment
- Evaluator Global Assessment
- EuroQol
- Assess Concomitant Medications

- Assess AEs

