11.5 Reporting

11.5.1 Adverse Events

All AEs that occur after signing the ICF will be recorded. At each visit during the trial, AEs that have occurred since the previous visit must be recorded. All subjects will be questioned and evaluated for

AEs or complications associated with the procedure. Complications of the injection include, but are not necessarily limited to: pain, swelling and/or inflammation at the injection site. The Investigator will determine the severity and relationship of each event, as defined above.

AEs observed during the course of this study, regardless of severity or relationship to the injection will be recorded on the appropriate eCRF. Each reported complication/AE will also include the duration, action taken to address the AE, and the resolution status (e.g. ongoing, resolved). These subjects will continue to be evaluated for safety and efficacy at all scheduled follow-up points.

The sponsor must report the results of an evaluation of an unanticipated adverse device effect (UADE) to relevant regulatory agencies and all reviewing ECs and investigators within timelines required by the regulatory agencies.

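### Rescue use between week 26 and a late 17-02 consent can go unrecorded, yet total use through week 39 is a tested secondary endpoint

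*Protocol*

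**What the plan says.** **Consent.** Protocol 10.2.1: "The subject will be asked to sign the ICF prior to attending the 39 week follow up visit". The Consent column in the 10.1 schedule carries no week or window. The synopsis gives the length of the extension: "The entire sub-study duration will be an additional 13 weeks".

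**Rescue supply.** Under Protocol 10.2.12.2, tablets from 16-02 "should be returned to the investigational site at the Cingal 16-02 26 week follow up visit". Tablets labelled for 17-02 are dispensed at the 17-02 Screening Visit.

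**Diary.** Protocol 10.3 puts diary hand-out at the 17-02 Screening Visit, and 10.2.13 also says Screening Visit. In the 10.1 schedule as extracted, the row "Distribute Subject Diary" is marked under 39 Weeks and its Consent cell is empty.

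**Pill count.** The week-39 list in 10.4 has "Count Rescue Medication Pills (if needed"). The schedule, 10.2.12.2 and an earlier paragraph of 10.4 call for the count without a condition.

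**Endpoint.** Protocol 7.2: "The usage of rescue medication through 39 weeks post treatment in the Cingal group compared to the TH group". It stands last in the hierarchical sequence of 12.1.2, which describes the Cingal quantity as total usage. SAP 4.1.3 does the same.

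**Adverse events and medications.** Protocol 11.5.1: "All AEs that occur after signing the ICF will be recorded". Protocol 10.2.12.3: "A medication is considered concomitant if taken after signing the ICF". Neither says whether the 16-02 or the 17-02 form is meant. Both sections also require each visit to ask back to the previous one.

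**The concern.** A total over 39 weeks is interpretable only if all 39 weeks are recorded. For a late consenter the plan stops one recording system at week 26 and starts the next at consent, with nothing specified between. The missing stretch differs by subject. It does not show up as a missing value either: the total simply comes out smaller.

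The two inconsistent entries add to this. A site that follows the schedule literally would hand out the diary at the visit where it is meant to be evaluated. A site that follows the 10.4 list could skip the pill count. At stake is the rescue-use comparison of Cingal with TH. To a lesser degree so is detection of disallowed treatment, because 10.2.12.1 monitors analgesics through the diary.

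**Working it through.** **Step 1: length of the extension.** 39 − 26 = 13 weeks, which reproduces the synopsis figure. With visit windows of ±1 week at both ends it runs from 38 − 27 = 11 to 40 − 25 = 15 weeks. As a share of the endpoint window, 13/39 = 33%.

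**Step 2: gap by consent date.** Let g = consent week − 26. The documents give no consent week, so the first column is an assumption.

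| Consent week (assumed) | g (weeks) | g/13 | g/39 |
|---|---|---|---|
| 26 | 0 | 0% | 0% |
| 28 | 2 | 15% | 5% |
| 30 | 4 | 31% | 10% |
| 34 | 8 | 62% | 21% |
| 38 | 12 | 92% | 31% |

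The form must be signed before the week-39 visit, so on nominal dates the limit is just under 13 weeks.

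**Step 3: effect on a total.** Assume, for illustration, a constant r tablets per week. The true total is 39r and the recorded total is r(39 − g), so the shortfall is g/39, the last column above. Dividing by recorded time gives r(39 − g)/(39 − g) = r. Under that assumption a rate is unaffected by the gap and a total is not.

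**Step 4: is there a rule for the gap?** Protocol 12.5 names WOMAC pain, WOMAC function and the Patient Global Assessment for imputation. Rescue use is not listed. SAP 4.1.3 and 4.5 add nothing for it.

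**Step 5: schedule marks.** The header has eleven visit columns. By position, diary distribution falls under Screening and 39 Weeks. The pill count falls under both Consent and 39 Weeks. The consent and enrolment-criteria rows do fall in the Consent column, so the extraction separates the last two columns. The table was machine-read, however, and the diary mark should be checked against the source.

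**Step 6: what the look-back covers.** Adverse events and new medications are assessed at 17-02 screening (10.3) and at week 39 (10.4), each reaching back to the previous visit (11.5.1, 10.2.12.3). That covers the interval by recall. Non-drug procedures for osteoarthritis have no explicit look-back question, although a procedure counts as treatment failure. The failure window itself differs: through week 39 in Protocol 2 and 12.1.3, through week 12 in SAP 4.1.4.

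**The case against.** The strongest reply is that consent near week 26 is implied. The extension is described as about 13 further weeks, the Consent column follows week 26, and 10.2.12.2 reads like a handover from one supply to the next. This makes a long gap less likely, but it sets no window. The synopsis offers the extension to subjects who have completed the 26-week follow-up, which allows consent afterwards.

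The diary mark may be one misplaced X, and the pill-count condition is one list item against several unconditional statements. Both points stand: these are contradictions to resolve, not the plan's only rule.

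Three stronger readings are tempting, and the documents do not support them:

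- A reader might infer that adverse events and treatment failures for weeks 26 to 39 go unrecorded. The look-back questions answer most of this. The same subject ID, the reuse of all 16-02 data and the extended database also point to one continuous record.
- A reader might infer that the whole extension record can be lost through consent at the week-39 visit. Section 10.2.1 requires signature before that visit, and the fractions above apply to rescue diary and pill data only.
- A reader might infer that missed failures would hide a treatment difference because they cluster in the less effective arm. Nothing in the documents links consent timing or missed failures to arm, and subjects and evaluators stay blinded.

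**Conclusion.** The point holds for rescue use. Following the plan as written can understate a subject's total by an amount that depends on when that subject consents: 0 to just under 13 weeks, or 0 to about 33% of the window. Consent at week 26 leaves no timing gap. How many subjects consent late is unknown, so the effect on the comparison cannot be sized, and no direction by arm is claimed.

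The result assumes that recording under 16-02 ends at week 26. The documents say so for the tablets but do not say what happens to the 16-02 diary.

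For adverse events and medications the weakness is narrower: reliance on recall, and a recording start tied to a consent form that is not named. Rescue use is the last secondary endpoint and treatment failure is exploratory. This is therefore a change that should be made, not a threat to the primary analysis.

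**What to change.** 1. **Protocol 10.2.1:** obtain 17-02 consent and hand out the diary at the 16-02 week-26 visit where that visit is still ahead. For later consenters, start the adverse-event, medication and osteoarthritis-procedure window at the week-26 visit and collect the interval retrospectively at consent.
2. **Protocol 11.5.1 and 10.2.12.3:** name the consent form that starts recording, consistent with item 1.
3. **Protocol 10.1:** after checking the source table, move the extension diary mark to the Consent column.
4. **Protocol 10.4:** delete the condition on the pill count.
5. **Protocol 12.1.2 and SAP 4.1.3:** analyse rescue use as pills per recorded day, and report recorded days by arm.
6. **Reconcile** the passages on rescue supply between the two studies (no supply rule is proposed here), and the treatment-failure window between protocol and SAP.

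The cost is protocol and SAP wording plus a few retrospective eCRF fields. Late consenters will bring some recall error. A rate also assumes that use in unrecorded time resembles use in recorded time, which should be stated.
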